2.4 RANDOMIZATION (OR STRATIFICATION) PROCEDURES

Patients with subclinical hypercortisolism will be randomized to adrenalectomy or observation as defined above and followed for 6 months. At the end of 6 months, the patients who were in the observation-only arm will all be offered an adrenalectomy. Patients with subclinical hypercortisolism tend to have high prevalence of metabolic consequences, specifically hypertension, diabetes, osteoporosis, hypercholesterolemia, and/or obesity. The patients will be randomized by the CRO.

To be conservative, the primary goal of this study will be to determine if the use of adrenalectomy is associated with 35% improvement vs. 5% improvement over 6 months without surgery as defined for any one or more of the following associated metabolic complications: hypertension, diabetes, osteoporosis, hypercholesterolemia, and/or obesity. With 31 patients per arm (62 total), there would be 80% power to detect a difference of this magnitude using a 0.05 significance level two-tailed Fisher's exact test.

Abbreviated Title: Subclinical Hypercortisolism**Version Date: 12/19/2016**

The following definitions will be used to determine if a given metabolic complication shows sufficient improvement in order to be considered as a component of a successful outcome:

Hypertension: normalization and/or improvement in blood pressure as assessed by reduction in pharmacotherapy and/or normalization of blood pressure (systolic pressure ≤ 140 and diastolic pressure ≤ 90) from baseline.

Diabetes: normalization and/or improvement in diabetes as assessed by normalization (A1C $< 6.5\%$), and/or reduction and/or discontinuation of pharmacotherapy.

Osteoporosis: an increase in the level of bone formation markers greater than the least significant change, which is calculated by multiplying the “precision error” of the specific biomarker by 2.77 (95% confidence interval) as per the National Osteoporosis Foundation (NOF) Clinician’s Guide to Prevention and Treatment of Osteoporosis 2013 ([Appendix D](#)).

Hypercholesterolemia: improvement in cholesterol as assessed by a reduction or elimination of pharmacotherapy and/or reduction in LDL levels to the optimal risk stratified goal as defined by ATP III guidelines ([Appendix E](#)).

Obesity: improvement in obesity as defined by a ten percent reduction in fasting morning weight compared to baseline.

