2.5.7.12 Fasting Triglyceride, total cholesterol, LDL, HDL levels

3 STUDY IMPLEMENTATION

3.1 STUDY DESIGN

This is a prospective randomized study of individuals with an adrenal mass less than or equal to 5 cm with biochemically confirmed hypercortisolism (2 out of 3: DST >3 mmol/l, elevated urine free cortisol, and/or morning ACTH <2.2 pmol/l) without overt clinical signs and/or symptoms (facial plethora, easy bruising, violaceous striae, and/or proximal muscle weakness) of excess cortisol. Individuals will undergo a clinical work up for an adrenal mass including laboratory and radiological studies (see below). Patients diagnosed with subclinical hypercortisolism and an adrenal mass less than 5 cm will be randomly assigned to either the non-operative or operative arm of the study. In patients found to have bilateral adrenal masses, the larger of the two masses will be treated as the adrenal lesion responsible for subclinical hypercortisolism. These patients with bilateral adrenal masses will be randomly assigned to either the non-operative or operative arm of the study. The responsible lesion will be adrenal mass that will be removed with a unilateral adrenalectomy or monitored. For patients in the non-operative or medical treatment-only arm, baseline evaluation will be undertaken, as well as follow up and re-evaluation every 3 months for 6 months, after which they will crossover to the operative arm and undergo an adrenalectomy. If a patient develops overt signs and symptoms of cortisol excess during the 6 months of observation, the tumor grows after enrollment during the 6 months of observation or 6 months have elapsed, the patient will cross over to the operative arm, and undergo an adrenalectomy. Worsening of metabolic complications will not be an indication for crossover. Patients after crossing over to the operative arm will have follow up every 3, 6, 9, and 12 months for the first year, six month follow up thereafter for the second year, and yearly follow up thereafter for three years. For a patient in the operative arm, the patient will undergo baseline evaluation, adrenalectomy, and follow up every 3, 6, 9, and 12 months for the first year, six month follow up thereafter for the second year, and yearly follow up thereafter for three years. At each follow-up visit, the patient will undergo repeat radiological and laboratory evaluation (see [Table 1](#)). Uniformity of medical management will be ensured by coordinating with primary care physicians, endocrinologists and the utilization of national guidelines in treating the metabolic manifestations and consequences of subclinical hypercortisolism.

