7 STATISTICAL CONSIDERATIONS

The primary objective of this study is to determine if the use of unilateral adrenalectomy is associated with normalization and/or improvement of hypertension, diabetes, osteoporosis, hypercholesterolemia, and/or obesity compared to medical treatment-only arm.

Patients with subclinical hypercortisolism will be randomized to adrenalectomy or medical treatment as defined above and followed for 6 months. At the end of 6 months, the patients who were in the medical treatment-only arm will all be offered an adrenalectomy. Patients with subclinical hypercortisolism tend to have high prevalence of metabolic consequences, specifically hypertension, diabetes, obesity and/or osteoporosis.

To be conservative, the primary goal of this study will be to determine if the use of adrenalectomy is associated with 35% who have improvement vs. 5% who improve over 6 months without surgery as defined for any one or more of the following associated complications: hypertension, diabetes, osteoporosis, hypercholesterolemia, and/or obesity. With 31 patients per arm (62 total), there would be 80% power to detect a difference of this magnitude using a 0.05 significance level two-tailed Fisher's exact test.

For the potential 31 patients initially randomized to observation and then undergoing an adrenalectomy at 6 months, the level of MAP, systolic, and diastolic pressure at 6 months but just before surgery will be compared to these values in the potential 31 patients initially randomized to immediate adrenalectomy 6 months after surgery using a Wilcoxon rank sum test. In addition, in the patients initially randomized to observation the changes in MAP from baseline to 6 months of observation as well as the declines in systolic and diastolic pressure from 6 months of observation until 6 months after surgery will be compared with a Wilcoxon signed rank test. Other important continuous parameters such as change in weight, triglycerides, total, HDL and LDL cholesterol, A1c, fasting glucose, and bone density may also be compared within patients using Wilcoxon signed rank test.

Abbreviated Title: Subclinical Hypercortisolism

Version Date: 12/19/2016

It is expected that 15-20 eligible patients may be able to enroll on this trial per year. In order to enroll 62 evaluable patients, it is anticipated that 3-4 years would be required. In order to allow for a small number of inevaluable patients, the accrual ceiling will be set at 66 patients.

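### Read literally, Section 7's supporting month-6 blood-pressure test admits only controls who then have surgery, so decliners and early crossovers could drop out of it after randomisation

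*Combined protocol and SAP*

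**What the plan says.** The rank sum test in Section 7 compares MAP, systolic and diastolic pressure. The control side is "For the potential 31 patients initially randomized to observation and then undergoing an adrenalectomy at 6 months", measured at 6 months just before the operation. The other side is "the potential 31 patients initially randomized to immediate adrenalectomy 6 months after surgery using a Wilcoxon rank sum test".

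The same section says that at 6 months "the patients who were in the medical treatment-only arm will all be offered an adrenalectomy", and Section 2.4 likewise says "the patients who were in the observation-only arm will all be offered an adrenalectomy". Section 8.6 requires a separate consent for any surgical procedure. The précis, Section 3.1 and Section 8.5 are firmer: they say that controls will cross over at 6 months.

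Section 3.1 also provides for surgery before month 6. One trigger begins "If a patient develops overt signs and symptoms of cortisol excess during the 6 months of observation"; the other is tumour growth. It adds: "Worsening of metabolic complications will not be an indication for crossover".

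The next sentence of Section 7 covers the within-patient tests. There the group is named without a surgery condition: "in the patients initially randomized to observation the changes in MAP from baseline to 6 months of observation".

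The document contains no intention-to-treat statement, no definition of analysis sets, and no rule for decliners, early crossovers or missing month-6 pressure.

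**The concern.** Randomisation protects a comparison when the groups compared are the groups randomised. Here membership of the control group can turn on whether the patient later accepts surgery, and on whether it happens at month 6 and not before. If acceptance is related to blood pressure, the remaining controls no longer mirror the surgery arm. A control whose pressure is well managed at month 6 might decline, and losing such patients would raise the control mean and favour surgery. Losing early crossovers with more active disease would push the other way.

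The surgery side has a milder form of the same problem: a patient assigned to surgery but never operated on has no reading 6 months after surgery.

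At stake is the only between-arm test of continuous blood pressure in the plan. The other continuous comparisons in Section 7 are within patients.

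**Working it through.** **1. The plan's own figure.** Section 7 states 80% power for 35% vs 5%, 31 per arm, two-tailed Fisher's exact test at 0.05. Summing the binomial probabilities of all tables with p ≤ 0.05 gives 80.9% at 31 per arm (78.8% at 30). The figure reproduces and is not in dispute. No power is stated for the blood-pressure test.

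**2. Who can fall outside the literal control set.**
- A control who declines. The month-6 visit is scheduled for all controls (Section 3.3.2), so a pre-surgery reading should exist and the surgery condition is not needed to obtain it.
- A control operated on before month 6. This patient has no unoperated month-6 reading, so a rule is needed.

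**3. Inputs for size.** From the documents: 31 per arm and a two-sided rank sum test; alpha 0.05 is taken from the primary test. Assumed, because the documents give neither: 10% to 20% declining (0.10 × 31 = 3.1 and 0.20 × 31 = 6.2, so k = 3 or 6, leaving 28 or 25 controls), and a correlation r between declining and lower pressure of 0, 0.3 or 0.5.

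**4. Approximate shift in the control mean.** If a fraction d with the lowest scores is removed, the mean of the rest rises by r × φ(z_d) / (1 − d) SD, where φ is the normal density and z_d the normal quantile at d.
- d = 0.10: 0.3 × 0.1755 / 0.9 = 0.058; 0.5 × 0.1755 / 0.9 = 0.097.
- d = 0.20: 0.3 × 0.2800 / 0.8 = 0.105; 0.5 × 0.2800 / 0.8 = 0.175.

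**5. Simulation under no treatment effect.** 100,000 trials per cell; pressure standard normal; 31 surgery patients against the remaining controls; the k controls lowest on the score removed. Monte Carlo error is about √(0.05 × 0.95 / 100,000) = 0.07 percentage points.

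| Decliners | r | Shift (SD) | Rejection |
|---|---|---|---|
| 0 | – | 0 | 4.8% |
| 3 | 0 | 0 | 4.8% |
| 3 | 0.3 | 0.054 | 5.4% |
| 3 | 0.5 | 0.091 | 6.5% |
| 6 | 0 | 0 | 5.0% |
| 6 | 0.3 | 0.098 | 6.4% |
| 6 | 0.5 | 0.164 | 9.4% |

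The shifts agree with step 4.

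**6. Early crossovers.** Suppose 1 or 2 also leave, with an assumed correlation of 0.3 with higher pressure. Alone they shift the control mean by −0.020 or −0.038 SD, with rejection 4.9% or 5.1%. Combined with the decliners above (r = 0.3 or 0.5), the net shift is 0.02 to 0.15 SD and rejection 5.0% to 8.5%.

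**7. Power if exclusion is unrelated to pressure.** At an assumed true effect of 0.75 SD, power is about 80%, 79% and 76% with 31, 28 and 25 controls.

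**8. Cost of keeping early crossovers with post-surgery readings.** Section 3.1 restarts the visit clock: "Patients after crossing over to the operative arm will have follow up every 3, 6, 9, and 12 months". A control operated on at month 4 is next seen at about 4 + 3 = 7 months. If m of 31 controls carry the full surgical effect, the contrast is multiplied by 1 − m/31. One gives 0.75 × 30/31 = 0.726 SD (3.2% smaller); two give 0.75 × 29/31 = 0.702 SD (6.5% smaller). Simulated power falls from about 80% to 77% or 75%.

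**The case against.** The strongest reply is that the phrase describes the arm and does not filter it. Section 7 speaks of a potential 31, which is the whole randomised arm. The précis, Section 3.1 and Section 8.5 all say that controls cross over. The next sentence uses the unrestricted label for a set of tests that includes changes from 6 months of observation to 6 months after surgery, which only operated patients can supply. The authors therefore seem to treat those randomised to observation and those later operated on as the same people. This reading is plausible. It does not settle the matter: Section 7 itself only offers surgery, the word potential allows for fewer than 31, and early crossover breaks the match even if every control is eventually operated on.

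The second reply is that no harm is shown. That stands. Both the decline rate and its link to pressure are assumed, and the low end of the range is close to nominal. Continuous blood pressure is also not among the secondary objectives in Section 1.1.2.

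A reader might infer that the test is biased towards surgery. The documents do not support this. Nothing in them ties refusal to pressure, the two kinds of exclusion can pull in opposite directions, and metabolic worsening is expressly not a reason for crossover. Harsher assumptions give larger figures (about 28% rejection with 30% excluded and r = 0.8), but the documents give no ground for them.

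**Conclusion.** The point holds as a defect of wording in a supporting analysis. On a literal reading, controls who decline or who cross over early can be excluded after randomisation, and unoperated patients in the surgery arm have no qualifying reading. If every control has surgery at month 6, nobody is lost on the control side. If exclusion is unrelated to pressure, there is no bias, only some loss of power. Under the assumptions in the working, the false-positive rate from decliners is about 5% to 9%.

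A reader might also infer that the main result of the trial is compromised. It is not: Section 7 does not attach the surgery condition to the Fisher comparison of 35% with 5%, and its stated power reproduces. Severity is low. The case for acting is that the analysis set is best fixed before data are seen and the correction is nearly free.

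**What to change.** Change Section 7 only. Replace the rank sum sentence with:

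> MAP, systolic and diastolic pressure at the month-6 visit will be compared by assigned arm among all randomised patients using a Wilcoxon rank sum test. Controls contribute their month-6 reading, taken before any surgery, whether or not they then have an adrenalectomy.

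Then add three rules:
- **Surgery-arm clock.** State whether month 6 runs from randomisation or from surgery. The text now counts from surgery, so a move to randomisation is a change of timepoint and should be disclosed as one; Section 3.4 sets no limit on the wait for surgery. If the clock stays at surgery, unoperated surgery-arm patients contribute the reading nearest 6 months after randomisation.
- **Early crossovers.** Report the result both ways: with the reading nearest 6 months after randomisation, and with the last reading before surgery. Which one leads is a choice of estimand and should be stated as such.
- **Within-patient tests.** Keep the restriction to operated controls for the signed-rank tests from 6 months of observation to 6 months after surgery, where it belongs.

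The cost is a few sentences, with no added patients, visits or tests. The downside is slight dilution if one or two early crossovers contribute off-schedule, post-surgery readings: power of about 77% or 75% in place of 80% at the assumed 0.75 SD. The analysis using their last pre-surgery reading shows how far this matters.

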3.4 SURGICAL GUIDELINES

After randomization, patients in the surgery arm will undergo an adrenalectomy as per standard of care.

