5.4 RESPONSE CRITERIA

For the purposes of this study, patients in the operative arm will be re-evaluated for response every 3 months from M0 to M12, every 6 months from M12 to M24, and then every 12 months thereafter through M60. Patients in the non-operative arm will be re-evaluated for response every 3 months from M0 to M18, every 6 months from M18 to M30, and then every 12 months thereafter through M66.

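### The between-arm blood-pressure comparison in Section 7 uses a different time origin in each arm and includes only patients who have surgery, and the plan never says what the operative M6 counts from

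*Combined protocol and SAP*

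**What the plan says.** Section 7 sets out a supplementary comparison of MAP, systolic and diastolic pressure. The control group is described as the patients randomised to observation who then have adrenalectomy at 6 months. Their "diastolic pressure at 6 months but just before surgery will be compared to these values" in the patients "initially randomized to immediate adrenalectomy 6 months after surgery using a Wilcoxon rank sum test".

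Section 3.4 is the only text on when the operative arm has surgery: "After randomization, patients in the surgery arm will undergo an adrenalectomy as per standard of care". It gives no maximum interval.

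The primary comparison in Section 7 is worded alike for both arms. Patients "will be randomized to adrenalectomy or medical treatment as defined above and followed for 6 months", and the target difference is "35% who have improvement vs. 5% who improve over 6 months without surgery". Section 2.4 says much the same. Neither states the day from which the 6 months run.

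For the visits themselves, Section 5.4 says that "patients in the operative arm will be re-evaluated for response every 3 months from M0 to M12". The calendar in Section 3.3.1 labels M0 as the baseline evaluation, which Section 2.5 places before randomisation.

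**The concern.** A randomised comparison is cleanest when both arms are read at the same time from randomisation and every randomised patient has a defined value. The blood-pressure comparison departs from this in two ways.

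- **Time.** The operative reading falls at 6 months plus the wait for surgery, and the control reading at 6 months. Any drift in pressure or in drug treatment over the wait enters the contrast.
- **Membership.** Both readings are defined by an operation. Whether and when a patient is operated on is decided after randomisation, so the groups compared need not be the groups randomised.

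A related gap touches the primary endpoint. Its components are read at calendar visits, and the operative M6 can be counted from more than one origin. The choice is left to the analyst.

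**Working it through.** **1. The plan's own figure.** Inputs from Section 7: 35% vs 5%, 31 per arm, two-tailed Fisher's exact test at 0.05. Power is the sum, over all pairs (x, y), of Bin(x; 31, 0.35) × Bin(y; 31, 0.05) for tables with Fisher p ≤ 0.05. The result is 80.9% (78.8% at 30 per arm), so the stated 80% reproduces. No time origin enters this calculation. Re-anchoring M6 leaves it unchanged, provided 35% is still expected with slightly shorter post-operative exposure.

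**2. What the operative 6-month reading counts from.**

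| Place | Origin |
|---|---|
| Sections 2.4 and 7, primary endpoint | not stated |
| Sections 3.3.1 and 5.4 | M0, the baseline evaluation before randomisation |
| Section 3.1 | lists baseline, adrenalectomy, then follow-up at 3, 6, 9 and 12 months; reads as from surgery |
| Section 7, blood pressure | surgery, explicitly |

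**3. Who has no value under the Section 7 blood-pressure definition.**

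- Controls who decline surgery. Sections 2.4 and 7 say surgery is offered at 6 months, although Sections 3.1 and 8.5 say that these patients cross over.
- Controls who cross over early. Section 3.1 provides for this if overt signs of cortisol excess develop or the tumour grows. They have no pre-surgical 6-month reading.
- Patients randomised to surgery who are never operated on.

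**4. Size of the clock difference.** The wait w (weeks) is an assumption. Time from randomisation = 6 + 7w/30.4375 months. The last two columns apply only if the primary endpoint were also read from surgery. They assume no surgical effect and an improvement rate that is constant and never reverses: h = −ln(1 − c)/26 per week, operative rate = 1 − exp(−h(26 + w)), with c the control rate.

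| w | Months from randomisation | Longer by | c = 5% becomes | c = 20% becomes |
|---|---|---|---|---|
| 0 | 6.0 | 0% | 5.0% | 20.0% |
| 1 | 6.2 | 3.8% | 5.2% | 20.7% |
| 2 | 6.5 | 7.7% | 5.4% | 21.4% |
| 4 | 6.9 | 15.3% | 5.7% | 22.7% |
| 8 | 7.8 | 30.7% | 6.5% | 25.3% |
| 12 | 8.8 | 46.0% | 7.2% | 27.8% |

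Even at 12 weeks, a move from 5% to 7.2% is small beside the planned 35% vs 5%. If unoperated patients worsen during the wait, the sign reverses.

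**5. Size of a measurement-setting difference.** The documents give neither a blood-pressure SD nor any pre-operative rise, so the shift is assumed in SD units. In 20,000 simulated rank sum tests per setting, with normal data, 31 per arm and no surgical effect, shifts of 0, 0.1, 0.2, 0.3 and 0.5 SD gave rejection rates of 4.6%, 6.2%, 11.4%, 19.4% and 47.3%. These show sensitivity only; they do not estimate what will happen.

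**6. The within-patient analysis.** Section 7 also tests "declines in systolic and diastolic pressure from 6 months of observation until 6 months after surgery" in the control arm, so the same M6 reading is its start point. An error d in that reading moves the change under observation by +d and the change after surgery by −d. Each test taken separately shifts by d. If the two changes were subtracted, the difference would shift by 2d. Section 7 names MAP for one change and systolic and diastolic pressure for the other, so separate tests are at least as natural a reading.

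**The case against.** A reader might infer that the trial's main 6-month result is biased in favour of surgery. The documents do not support that, for four reasons.

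- **Scope.** The mismatched rule governs one supplementary blood-pressure test that has no power statement. The primary text treats both arms alike.
- **Prompt surgery.** The same sentence calls the operation immediate. The calendars fit surgery near M0: the control M9 visit carries the tests of the operative M3 visit, and the control schedule in Section 5.4 is the operative one moved by 6 months (M12, M24 and M60 become M18, M30 and M66). On that convention the operative M6 is about 6 months after surgery.
- **Direction.** Section 1.2 describes an observational comparison in which unoperated patients worsened in blood pressure (50%), fasting glucose (37.5%) and LDL (50%). Section 8.5 expects possible worsening under observation. Waiting could therefore disadvantage the operative arm.
- **Setting.** It is tempting to read the control value as one taken at the surgical admission. The pre-operative label in Section 3.3.2 covers M3 as well as M6, so it marks a study phase. Reading controls before crossover surgery is also necessary to keep the operation out of the control value.

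All four stand, and they limit the point. They do not remove it. Calling surgery immediate sets no window, and the convention is inferred from the calendars. Section 7 does not say that its control reading is the scheduled M6 visit, and no section requires the same blood-pressure conditions in both arms. The missing values listed in the working depend on neither the wait nor any rise in pressure.

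**Conclusion.** The point holds for the between-arm blood-pressure comparison: the time anchors differ, the difference has no stated limit, and patients are selected on having surgery. For the primary endpoint it is a gap in definition: 6 months is stated, but its origin is not.

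The size cannot be fixed from the documents. It is small if surgery is prompt (under 8% longer follow-up at an assumed wait of 2 weeks or less) and grows with the wait. The direction is open. Claims that the design favours surgery, or that control pressures will be raised by impending surgery, rest on assumptions that the documents neither make nor support. The stated primary power is unaffected. This is a cheap improvement, not a threat to the main conclusion.

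**What to change.** - In Sections 2.4, 5.4 and 7, define M6 as 6 months after randomisation in both arms, with one common visit window, for every randomised patient in the arm assigned. This covers both the primary endpoint and the between-arm blood-pressure comparison.
- State that the control value is the scheduled M6 study visit, measured under the same conditions as the operative M6 visit. For controls still under observation, this visit precedes the crossover operation.
- Use that same value as the start point of the within-patient analysis.
- Keep 6 months after surgery as a secondary time point.

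The cost is wording, since both calendars already contain an M6 visit. Operated patients will have slightly under 6 post-operative months at M6. Controls who cross over early will contribute a post-operative value at M6, which may dilute the contrast but preserves the randomised comparison. The text should make clear that their M6 visit is kept when their follow-up restarts from surgery.

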8.5 RISKS/BENEFITS ANALYSIS

The main risk of participation is related to the risk of complications in the adrenalectomy arm and worsening of the metabolic complications in patient in the observation arm. The risk of

Abbreviated Title: Subclinical Hypercortisolism

Version Date: 12/19/2016

adrenalectomy is less than 1% which would outweigh the potential benefit of reversal of metabolic complications. In patients in the observation arm, there may be worsening of the metabolic complications but all patients will cross over to the adrenalectomy arm after 6 months of follow up and will be medically treated as standard of care for the metabolic complications.

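### Supportive continuous analyses: month-6 blood pressure is compared between arms without the baseline value, and the other continuous measures have no between-arm test

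*Combined protocol and SAP*

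**What the plan says.** The primary analysis (sections 2.4 and 7) is a two-tailed Fisher's exact test at 0.05 on a composite of improvement in any of five metabolic complications, with 31 patients per arm.

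Section 7 then adds analyses of continuous measures, without calling them secondary or exploratory:

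- **Pressure, between arms.** The observation group is introduced as "For the potential 31 patients initially randomized to observation and then undergoing an adrenalectomy at 6 months". Its mean arterial, systolic and "diastolic pressure at 6 months but just before surgery will be compared" with "these values in the potential 31 patients initially randomized to immediate adrenalectomy 6 months after surgery using a Wilcoxon rank sum test". The variable is the level at month 6; no baseline value enters.
- **Pressure, within the observation arm.** Signed rank tests are planned. This is the only place where section 7 uses baseline pressure.
- **Other measures.** Weight, triglycerides, total, HDL and LDL cholesterol, A1c, fasting glucose and bone density "may also be compared within patients using Wilcoxon signed rank test". No between-arm test is named.

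The data for a randomised comparison are mostly already planned. Vital signs and weight are taken before randomisation (2.5, 2.5.1), as are A1c, fasting glucose and lipids (2.5.7). The calendars in 3.3.1 and 3.3.2 schedule A1c, fasting glucose and lipids at M6 in both arms. The primary endpoint itself needs pressure and weight at 6 months.

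Section 3.1 allows surgery before month 6 if overt signs appear or if "the tumor grows after enrollment during the 6 months of observation". Sections 2.4 and 7 say that at 6 months "the patients who were in the observation-only arm will all be offered an adrenalectomy", whereas section 8.5 says that "all patients will cross over to the adrenalectomy arm after 6 months of follow up and will be medically treated as standard of care".

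**The concern.** There are three parts.

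1. **Unused baseline.** A comparison of month-6 levels leaves between-patient variation in the error term that the pre-randomisation reading could remove. With 31 per arm this can matter.
2. **No randomised contrast.** Section 1.2 criticises earlier studies for lacking randomisation and uniform medical management. Drug treatment runs alongside surgery here too: "Uniformity of medical management will be ensured by coordinating with primary care physicians". A before-after change therefore mixes surgery, drug treatment and regression to the mean, and only the other arm can separate them. Fasting glucose, triglycerides, total and HDL cholesterol have no between-arm comparison at all. Weight, A1c and LDL reach one only as dichotomised parts of the composite.
3. **Group wording.** Read literally, the phrase about then undergoing adrenalectomy at 6 months would remove early crossovers and patients who decline. That selection happens after randomisation and depends partly on the course of disease. An early crossover also has no value at 6 months just before surgery, and section 7 gives no rule for that patient.

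At stake is how well the trial can describe the size of any effect on pressure, glucose, lipids and weight, which an any-one-of-five composite cannot show. The primary conclusion is not at stake.

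**Working it through.** **Plan's own figure.** Exact enumeration of Fisher's test, 35% vs 5%, two-sided 0.05: power is 78.8% at 30 per arm and 80.9% at 31. The stated 80% is reproduced, and nothing below changes it. The plan gives no power figure for the continuous analyses.

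**Inputs.** From the documents: n = 31 per arm. Assumed, because the documents give none: the correlation r between baseline and month 6, SD 15 mmHg, and true differences d of 5, 8 and 12 mmHg.

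**Interval width.** Adjustment multiplies the residual SD by √(1 − r²), so the large-sample narrowing is 1 − √(1 − r²). With 31 per arm there is a small penalty for the lost degree of freedom and chance baseline imbalance.

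| r | √(1 − r²) | Large-sample narrowing | With 31 per arm | Equivalent unadjusted n per arm, 31/(1 − r²) |
|---|---|---|---|---|
| 0.3 | 0.954 | 4.6% | 3.7% | 34.1 |
| 0.5 | 0.866 | 13.4% | 12.6% | 41.3 |
| 0.7 | 0.714 | 28.6% | 27.9% | 60.8 |

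At r = 0.2 the narrowing with 31 per arm is only 1.1%.

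For scale, the unadjusted standard error at SD 15 is 15 × √(2/31) = 3.81 mmHg, giving a half-width of 1.96 × 3.81 = 7.47 mmHg.

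**Power.** Simulation of 10,000 bivariate-normal trials per setting, SD 15, r = 0.5:

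| d (mmHg) | Rank sum | Rank ANCOVA | Like-for-like gain | Ordinary ANCOVA |
|---|---|---|---|---|
| 5 | 24.1% | 30.1% | 6.0 points | 32.1% |
| 8 | 51.6% | 62.5% | 10.9 points | 65.9% |
| 12 | 85.2% | 92.2% | 7.0 points | 94.1% |

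Type I error was 4.6% to 5.3% for all three methods over r = 0.2 to 0.7. The like-for-like column isolates the baseline value. Moving to ordinary ANCOVA gains 8.0, 14.3 and 8.9 points, but part of that comes from dropping ranks when the data are normal.

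**Why not a change score.** Its variance relative to the month-6 level is 2(1 − r): 1.4 at r = 0.3, 1.0 at 0.5 and 0.6 at 0.7. Below r = 0.5 it is worse than ignoring baseline. ANCOVA's ratio, 1 − r², is 0.91, 0.75 and 0.51.

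**Literal group wording.** If k of 31 patients are dropped and their mean differs by δ mmHg from that of the rest, the arm mean shifts by kδ/31. With assumed k = 1 to 5 and δ = 5 to 15, this runs from 1 × 5/31 = 0.16 to 5 × 15/31 = 2.42 mmHg, against the 7.47 mmHg half-width.

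**The case against.** The strongest reply is that the planned rank-sum test is valid, that no objective in section 1.1 names pressure, glucose, lipids or weight as a continuous outcome, and that preferring ANCOVA is a matter of efficiency. This stands as far as it goes: the loss for pressure is precision, not bias. It does not answer the missing between-arm test for the other measures.

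Four further points limit the concern.

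- **Size.** Every gain rests on assumed values and is small at low correlation. The rank-to-rank gain is the fair figure; the larger rank-sum-to-ANCOVA figure mixes two changes.
- **Group wording.** A reader might infer that the plan analyses only patients operated on at month 6. The text does not support that as the intended meaning: both groups are described as initially randomised, and 31 is the full arm size in the power statement. The literal reading remains possible because early crossover is allowed and surgery is offered. The statements that all patients will cross over (précis, 3.1, 8.5) make refusal look unlikely but do not exclude it.
- **Medication.** Reduced drug treatment counts as success in the composite. If drugs are cut after surgery, month-6 levels understate the effect, with or without baseline adjustment. This stands, and the fix must address it.
- **Mixed population.** Patients need a metabolic complication to enter, but not a particular one, and section 1.2 cites hypertension prevalence of 33% to 89%. An all-patient pressure model includes people without hypertension, so the assumed differences may be optimistic.

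Quality of life, a secondary objective set against medical therapy, also has no named test. That is a separate gap, and the operative calendar has no M6 questionnaire.

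**Conclusion.** The point holds in a limited form. Section 7's comparison of month-6 pressure is valid but leaves out a baseline value that the trial collects. For the other continuous measures, section 7 names no comparison of the randomised arms. The second part needs no assumed figure. The first costs about 4%, 13% or 28% of interval width at r = 0.3, 0.5 or 0.7, and about 6 to 11 points of power like for like at r = 0.5, SD 15 and differences of 5 to 12 mmHg.

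Two stronger readings are not supported. One is that the primary result or the sample size is compromised: the Fisher calculation reproduces and is untouched. The other is that weight, A1c and LDL never reach a randomised comparison: they do, as dichotomised components of the composite. The group wording is an ambiguity to remove, not evidence of a biased analysis.

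**What to change.** In section 7:

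1. Define both groups as all patients randomised to the arm, analysed as randomised, with early crossovers and patients who decline surgery kept in their assigned arm.
2. For mean arterial, systolic and diastolic pressure, weight, triglycerides, total, HDL and LDL cholesterol, A1c and fasting glucose, pre-specify one between-arm ANCOVA of the month-6 value on assigned arm and baseline value. Report the adjusted difference with its 95% CI. Label these ten estimates exploratory, without multiplicity control.
3. Choose any transformation in advance (for example log triglycerides), not after looking at skewness. Keep the planned rank-sum test for pressure as a sensitivity analysis.
4. Use the visit nearest 6 months from randomisation in both arms, including for early crossovers. For observation patients operated on at month 6, this is the pre-operative M6 visit. For early crossovers, use the last pre-surgery value as a sensitivity analysis. Report time from randomisation by arm, because section 5.4 counts operative visits from M0, section 7 counts from surgery, and section 3.4 gives no interval to surgery.
5. Report medication change by arm beside each estimate, because drug reduction can mask a difference in levels.
6. Keep the signed rank tests as descriptive. Leave bone density out of the month-6 models, because DEXA is not scheduled at M6 in either arm.

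The cost is revised wording, slightly more analysis and several exploratory estimates to report. No visit, test or patient is added.
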